## 5.5. PATIENT-REPORTED OUTCOMES

### 5.5.1. Respiratory Infection Intensity and Impact Questionnaire (RiiQ™v2)

For the second and third RSV season, only the total RiiQ Respiratory and Systemic symptom score change from Day 365/Day 730 and the respective AUC will be calculated for RSV ARIs, occurring during the second or third RSV season. For details in calculations see Section 4.5.1.

To align with the phase 3 VAC18193RSV3001 study, also the RiiQ Lower Respiratory Symptom scores (cough, short of breath, coughing up phlegm (sputum) and wheezing) and the respective AUC will be calculated for RSV ARIs during the second and third RSV season. Post-hoc analysis will be done for the first RSV Season.

#### 5.5.1.1. Analysis Methods

The number of observations, median, first and third quartile (q1, q3), minimum and maximum of the AUC will be calculated and graphically presented with boxplots per group, for any RSV ARI, RSV A ARI and RSV B ARI (based on the DDL assay) and for Case Definition 1 occurring during the second or third RSV season and across the three RSV seasons.

Scatterplots of the AUC values versus the duration of the ARI episodes will also be created, for any RSV ARI and for Case Definition 1 occurring during the second or third RSV season and across the three RSV seasons.

Note that the AUCs for RSV ARIs occurring during the first RSV season are defined based on the change from baseline (Day 1) and the AUCs for ARIs occurring the second or third RSV season are defined based on the change from Day 365/Day 730 (see Section 2.1). In case a participant experience two or more RSV ARIs during the three seasons, the same rule will apply similar to a participant experiencing two or more ARIs during the same season (see Section 4.5.1.1).

### 5.5.2. Patient Global Impression Scores

The scoring of the Patient Global Impression of Health (PGI-H) will be updated to align with the Phase 3 studies. Participants report their overall impression of their health status today on the following scale: 0=Very good, 1=Good, 2=Fair, 3=Poor, 4=Very poor.

For the second and third RSV season, the same scores will be collected, as in the first RSV season. In addition to the scores indicated in Section 4.5.2, the AUC for the change from Day 365/Day 730 for PGI-H and the AUC for PGI-C and PGI-S, will be calculated.

#### 5.5.2.1. Analysis Methods

The following analysis will be conducted for any RSV ARI, RSV A ARI and RSV B ARI (based on the DDL assay) and in case of the AUC analyses additionally for RT-PCR-confirmed RSV-A-

mediated LRTD and RT-PCR-confirmed RSV-A-mediated LRTD based on Case Definition 1 occurring during the second or third RSV season and across three RSV seasons.

For the AUCs the number of observations, median, first and third quartile ( $q_1$ ,  $q_3$ ), minimum and maximum will be calculated and graphically presented with boxplots per group.

Moreover, the number of days a participant took to return to its usual health will be summarized and graphically presented with Kaplan Meir curves. Hazard ratios will also be calculated, with a cox proportional hazard model with time to return to usual health as dependent variable and group as independent variable.

In case a participant experiences two or more RSV ARIs during the three RSV seasons, the same rule will apply similar to a participant experiencing two or more ARIs during the same season (see Section 4.5.1.1).

## **5.6. Lawton-Brody Instrumental Activities of Daily Living (IADL) Scale**

See Section 4.6.

### **5.6.1. Analysis Method**

For all participants with any RT-PCR-confirmed RSV disease from the PPE set during the first (up to Day 365) or second RSV season (up to Day 730), descriptive statistics of the actual values of the IADL score will be tabulated by sex and group for Day 1 (baseline), Day 365 and Day 730.

## **5.7. Clinical Assessment**

See Section 4.8.

### **5.7.1. Analysis Methods**

Clinical assessments will be analyzed similarly to the first RSV season, as described in Section 4.8.1, for the second or third RSV season and across the three RSV seasons, for participants with any RT-PCR confirmed RSV disease.

Vital signs will only be summarized across the three RSV seasons, for participants with any RT-PCR confirmed RSV disease. An abnormality will be considered as emerging in a particular period if it is worse than the baseline value of the corresponding season.

For ARIs collected during the second or third RSV season, change from the Day 365/Day 730 will be calculated instead of the change from baseline.

In case a participant experience two or more RSV ARIs during the three RSV seasons, the same rule will apply similar to a participant experiencing two or more ARIs during the same season (see Section 4.5.1.1).

## 5.8. Clinically Relevant Diseases

Clinical relevant diseases associated with RSV ARIs as defined in the phase 3 VAC18193RSV3001 study will be analyzed:

- Hospitalization
- Emergency department visit (as assessed on the eCRF medical encounters form and MRU pages [emerging MRU to be summarized])
- At least one of the following complications: asthma, COPD, respiratory distress, bronchitis, bronchial hyperreactivity, CHF, cardiac arrhythmia, renal impairment or the presence of X-ray or radiological confirmed pneumonia, respiratory arrest and/or failure, pulmonary embolism, pleural effusion, atelectasis, acute coronary events, acute cerebrovascular events, altered mental status, seizure, syncope, systemic inflammatory response syndrome (SIRS), new neurological deficit, asthenia, dehydration or metabolic disturbances.  
See [Attachment 10](#) for the complication terms. These terms will be reported in the AE domain.  
Asthma and chronic obstructive pulmonary disease (COPD) exacerbation supporting LRTD reported in the medically attended ARI form will also be counted, as well as X-ray or radiological confirmed pneumonia from the diagnostic tests form.
- Decreased oxygen saturation defined as oxygen saturation of <92% for participants with a baseline oxygen saturation of  $\geq 92\%$  at randomization; for participants with baseline oxygen saturation <92%, decreased oxygen saturation is defined as a  $\geq 3\%$  decrease in their oxygen saturation from baseline
- Tachypnea (at least Grade 2, see Section 4.8)
- Need of supplemental oxygen
- Hypotension (at least Grade 3, see Section 4.8)
- Pulmonary function test results supporting diagnosis of LRTD
- Arterial blood gas results supporting diagnosis of LRTD

### 5.8.1. Analysis Methods

The PPE set will be used to analyze all clinically relevant diseases.

For the second and third RSV season and across season two and three and across all three RSV seasons, the following will be calculated. The proportion of participants with any RT-PCR confirmed RSV disease leading to clinically relevant diseases (as defined in Section 4.9 and 5.8) leading to clinically relevant diseases will be tabulated per group and the corresponding VE (1-relative risk) with a 95% CI will be determined and graphically depicted with a forest plot. A Poisson model similar to the primary endpoint will be used.

Any RT-PCR confirmed RSV disease leading to clinically relevant diseases as defined in Section 5.8 will also be summarized for the first RSV season.

The different subcategories of the clinically relevant diseases will be summarized only across the three RSV seasons, for participants with any RT-PCR confirmed RSV disease and RT-PCR-confirmed RSV-mediated LRTD based on Case Definition 1.

In case a participant experiences two or more RSV ARIs during the three RSV seasons, the same rule will apply similar to a participant experiencing two or more ARIs during the same season (see Section 4.5.1.1).

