#### **4.4.2.1.2. RSV RT-PCR Confirmation of the Considered ARI Episode**

Confirmation of RSV infection by RT-PCR (in midturbinate swabs or sputum sample, whenever available) will be performed at the central laboratory (GeneXpert assay only). For participants hospitalized with symptoms of an ARI, confirmation of RSV infection using an FDA-approved RT-PCR test at the local (hospital) laboratory will also be used for the analysis of case definitions if results from the central laboratory are not available. One positive sample (defined as any sample with a value above the limit of detection) is sufficient. RT-PCR results from samples that were out of stability are excluded from the analysis, regardless if they were RSV positive or RSV negative (except for the analysis based on the FAS).

Any midturbinate nasal swab and/or sputum sample taken within 7 days after onset of an ARI episode or during the ARI episode will be allocated to that ARI. In case of 2 consecutive ARI episodes, where the second ARI starts within 7 days after the onset of the first episode and the ARI Day 3-5 sample of the first episode is taken while the second episode is ongoing, then the midturbinate nasal swab and/or the sputum sample will be attributed to both ARIs.

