#### 4.5.1.1. Analysis Methods

RiiQ scores will be analyzed based on the PPE set, with a major focus participants with any RT-PCR disease (see [above](#) for definition) .

For the **total scores**, number of observations, mean, standard error, median, first and third interquartile will be tabulated and means with standard errors will be graphically presented per group and time point for changes from baseline. Moreover, the relationship of the baseline total scores and the worst score reported during the ARI episode will be explored with scatterplots. Furthermore, descriptive statistics of the baseline, the end of season and the change between these two timepoints will be calculated for all participants based on the PPE set, for participants with any RT-PCR-confirmed RSV disease and for participants meeting each of the primary endpoints separately, based on the PPE set.

For the **AUCs** number of observations, median, first and third quartile (q1, q3), minimum and maximum will be calculated and graphically presented with boxplots per group. Scatterplots of the AUC values versus the duration of the ARI episodes will also be created.

**Note 1:** Everything reported until the resolution of an ARI will be used.

In case two or more assessments are reported at the same day (for example ARI Day 3-5 eDiary and eDevice or two assessments at the same device) then the worst total score will be used. The same applies for the AUC calculations too.

In case a participant experiences two or more ARIs (based on the ‘Any ARI’ definition, Section 4.4.3.1) during the study then the following rules will be followed in identifying which ARIs data will be used:

- If all fulfil a case definition, then data from the RT-PCR confirmed RSV disease fulfilling the strictest definition will be used (case definition 1 > case definition 2 > case definition 3)
- If only one fulfils a case definition, then those data will be used
- If none fulfils a case definition or all fulfil the same case definition, then data from the first RT-PCR confirmed RSV disease will be used.
- If none is a RT-PCR confirmed RSV disease, then use:
  - the ARI that fulfils the strictest case definition based on symptoms only (case definition 1 > case definition 2 > case definition 3) Or
  - the first ARI, in case 2 or more fulfil the same case definition on symptoms only or in case they do not fulfil any case definition on symptoms only.

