- **First occurrence of any RT-PCR-confirmed RSV A ARI, based on the DDL assay**
- **First occurrence of any RT-PCR-confirmed RSV B ARI, based on the DDL assay**
- **First occurrence of RT-PCR-confirmed RSV-A-mediated LRTD according to Case Definition 1, based on the DDL assay**
- **First occurrence of RT-PCR-confirmed RSV-B-mediated LRTD according to Case Definition 1, based on the DDL assay**
- **First occurrence of potential complications (according to the Phase 3 definition; see Section 5.8) of respiratory disease linked to an RT-PCR confirmed RSV ARI**
- **First occurrence of hospitalization linked to an RT-PCR confirmed RSV ARI**
- **First occurrence of pneumonia linked to an RT-PCR confirmed RSV ARI**

Pneumonia is defined as:

- X-ray confirmed pneumonia (as assessed on the eCRF diagnostic tests form: diagnosis of pneumonia confirmed by chest X-ray) *OR*

- Radiological confirmed pneumonia (as assessed on the eCRF diagnostic tests form: diagnosis of pneumonia confirmed by chest X-ray, CT-scan or MRI)

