### **5.10.1. Analysis Methods**

The PPE set will be used to analyze the medical resource utilization data.

At Day 365 and Day 730 the proportion of participants reporting having used the medical resources by category and subcategory will be summarized per group and per risk level.

The proportion of participants with emerging medical resources utilized, associated with any RT-PCR confirmed RSV ARI or LRTD based on Case Definition 1 across all three RSV seasons, will be summarized per group and per risk level, by MRU category and subcategory. Moreover, for those participants, the number of recorded visits and the length of stay will also be summarized descriptively for the RSV ARI episode.

Finally, the proportion of participants with any RT-PCR confirmed RSV disease with emerging medial resources utilized will be tabulated per group and the corresponding VE (1-relative risk) will be determined as described in Section 5.4.1.2 and graphically depicted with a forest plot, for the second and third RSV season and across season two and three and all three RSV seasons. In case a participant experience two or more RSV ARIs during the three RSV seasons, the same rule will apply similar to a participant experiencing two or more ARIs during the same season (see Section 4.5.1.1).

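### For the VE on clinically relevant disease and medical resource use, the SAP counts the first event in any RSV ARI but also restricts each participant to one selected ARI, and does not say which governs

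*SAP*

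**What the plan says.** Section 5.8.1 plans, for season two, season three, both together and all three seasons, that the proportion of participants with any confirmed RSV disease leading to clinically relevant disease "will be tabulated per group and the corresponding VE (1-relative risk) with a 95% CI will be determined", using a Poisson model like that of the primary endpoint. Section 5.10.1 plans a VE for emerging medical resource use over the same periods and refers to Section 5.4.1.2 for the method. There, follow-up ends at the first event of the endpoint under study.

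Both sections also carry a multiple-ARI instruction. In 5.8.1 it closes the section: "In case a participant experiences two or more RSV ARIs during the three RSV seasons, the same rule will apply". In 5.10.1 it follows the VE sentence in the same paragraph: "In case a participant experience two or more RSV ARIs during the three RSV seasons, the same rule will apply". Each points to Section 4.5.1.1, which selects one ARI as follows:

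- If all ARIs meet a case definition, "then data from the RT-PCR confirmed RSV disease fulfilling the strictest definition will be used".
- "If only one fulfils a case definition, then those data will be used".
- If none meets one, or "all fulfil the same case definition, then data from the first RT-PCR confirmed RSV disease will be used".

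Among the other exploratory endpoints, Section 5.4.1.1 lists "First occurrence of hospitalization linked to an RT-PCR confirmed RSV ARI", with no selection of ARIs.

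**The concern.** Strictness under 4.5.1.1 depends on the case definitions in Table 6, which count LRTI and systemic symptoms. Hospitalisation, complications and resource use play no part in the choice of ARI. Picking one ARI makes sense for a symptom score or an AUC, which needs a single curve. An event endpoint needs no such choice, and choosing can discard the episode in which the event happened.

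Two consequences follow if the rule is applied to the VE. A participant can be a case for hospitalisation but not for a composite whose first listed component in Section 5.8 is hospitalisation. Also, events can be lost only in participants with repeat RSV ARIs. If the vaccine works, these are mainly placebo recipients, so VE would be pulled towards zero.

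**Working it through.** The SAP gives no figure on this point, so there is none to reproduce.

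**Step 1: one participant under each instruction.** Take an RSV ARI in season one meeting Case Definition 1 without hospitalisation, then one in season three meeting Case Definition 1 with hospitalisation.

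- First event under 5.4.1.2, three seasons: a case, dated in season three.
- One-ARI rule of 4.5.1.1: both meet the same definition, so the season-one ARI is kept. If it has no other qualifying component, the participant is a non-event.
- Hospitalisation endpoint in 5.4.1.1: a case.

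The first two results cannot both define the same VE. The rule also spans all three seasons, while 5.8.1 and 5.10.1 plan single-season VEs too. How a season-one ARI should bear on a season-three VE is not stated.

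**Step 2: how often the rule drops the event, by pattern.** With two RSV ARIs, each at one of four levels (Case Definition 1, 2, 3 or none), and exactly one hospitalised, there are 4 × 4 × 2 = 32 patterns. The 12 unequal pairs each lose the hospitalised ARI once, when it has the lower level. The 4 ties each lose it once, when it comes second. That is 12 + 4 = 16 of 32. This counts patterns and is not a probability. If any qualifying ARI counts, the number lost is 0.

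**Step 3: how many participants could be affected.** Inputs: N = 2,900 per group (Table 1) and VE 70% (planning value in Table 4). The RSV ARI rate per season is not given. I assume r = 0.75% to 3%; the lower end is the planning incidence in Table 4, where events are Case Definition 2 cases. With a Poisson number of RSV ARIs over three seasons, λ = 3r on placebo and 0.3 × 3r on vaccine, and

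expected number with two or more = N × [1 − e^(−λ)(1 + λ)].

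| r per season | placebo, ≥1 RSV ARI | placebo, ≥2 | vaccine, ≥2 |
|---|---|---|---|
| 0.75% | 64.5 | 0.7 | 0.07 |
| 1.5% | 127.6 | 2.8 | 0.26 |
| 3% | 249.6 | 11.1 | 1.0 |

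This ignores the truncated follow-up of Revaccination Subcohorts A and B, so it is on the high side for any given rate.

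**Step 4: expected events lost.** Assume 25 placebo participants with a qualifying event, that two ARIs in one person qualify independently with probability q = 25 / (number with ≥1), and that half of discordant pairs lose the event. Expected losses are then (number with ≥2) × q(1 − q):

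- 0.75%: q = 0.388; 0.72 × 0.237 = 0.17
- 1.5%: q = 0.196; 2.85 × 0.158 = 0.45
- 3%: q = 0.100; 11.1 × 0.090 = 1.0

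**Step 5: effect on VE**, equal follow-up and assumed counts:

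- 8 v 25: 1 − 8/25 = 68.0%. One placebo event lost: 1 − 8/24 = 66.7%. Two lost: 1 − 8/23 = 65.2%.
- 4 v 14: 1 − 4/14 = 71.4%. One lost: 1 − 4/13 = 69.2%. Two lost: 1 − 4/12 = 66.7%.

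**The case against.** The strongest reply is that the VE text already points to the right answer. Section 5.8.1 speaks of any confirmed RSV disease leading to clinically relevant disease and borrows the primary model. Section 5.10.1 refers to 5.4.1.2. Both imply that the first qualifying event counts, in whichever ARI. In 5.8.1 the multiple-ARI sentence comes after the paragraph on subcategory summaries and does not mention VE. The comparable VE analyses in 4.9.1, 4.10.1 and 5.9.1 state no selection rule. This stands as a competing reading, so a reader should not infer that the SAP definitely turns such a participant into a non-event. It does not remove the conflict: no text exempts the VE from the rule, and in 5.10.1 the rule comes straight after the VE.

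Two other stronger readings are not supported.

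- One might say that a RiiQ rule was carried over by accident. The SAP also writes the rule out in full for clinical assessment (4.8.1) and for medical resource use (4.11.1), so it is a deliberate choice in those places.
- One might say that a single illness split into two consecutive ARIs would commonly lose its hospitalisation, because under 4.4.2.1.2 "the midturbinate nasal swab and/or the sputum sample will be attributed to both ARIs". That provision covers only a second ARI starting within 7 days of the first one's onset, with the first one's Day 3-5 sample taken while the second is ongoing. The SAP does not say that a hospitalisation would be linked to the second ARI. If the second met a stricter definition, the rule would keep it.

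It is also fair to say that few participants are affected. Section 5 itself expects that RSV cases may be limited in seasons two and three. Hospitalisation remains intact as its own endpoint.

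**Conclusion.** The point holds as an unreconciled conflict between two instructions for the same VE, clearest in Section 5.10.1. Applied literally, the one-ARI rule can miscount a participant whose unselected RSV ARI carried the hospitalisation or resource use, and the composite then disagrees with the hospitalisation endpoint. If the vaccine works, losses fall mainly on placebo and pull VE slightly towards zero. Under the assumptions above, about one placebo event or fewer would be lost, a shift of roughly one to two percentage points in the illustrations; with no repeat RSV ARIs the effect is nil. The rates, event counts, independence and one-half loss share are my assumptions, not the SAP's. The endpoints are exploratory and the primary analysis is untouched. A clarification is worth making because it is cheap and removes a rule that can miscount cases.

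**What to change.** In Sections 5.8.1 and 5.10.1, state that for the proportion and VE analyses a participant is a case if any RSV ARI within the analysed season(s) leads to clinically relevant disease (or emerging medical resource use). Date the event at the onset of the first such ARI, consistent with 5.4.1.2.

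Leave the one-ARI rule of 4.5.1.1 unchanged for the descriptive scores, AUCs and clinical-assessment summaries, and for the placebo relationship analyses. Removing it there would leave those analyses without a rule for repeat ARIs.

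The cost is a sentence in each section and a small change in derivation, with no new data. One caution: third-season surveillance ended on 15 April 2022 (Section 5.14), Amendment 7 is dated 11 July 2022, and the analysis in Section 3.6 is on unblinded data. The clarification should therefore be dated and recorded as a change to the planned analysis.

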## **5.9. Therapeutic Interventions**

See Section 4.10.

### **5.9.1. Analysis Methods**

The PPE set will be used to analyze the therapeutic interventions. A similar analysis to derive VE as in the first RSV season, limited to any RSV ARI, will be repeated for the second and third RSV season and across season two and three and all three RSV seasons.

The different subcategories of new therapeutic interventions will be summarized only across the three RSV seasons, for participants with any RT-PCR confirmed RSV disease and RT-PCR-confirmed RSV-mediated LRTD based on Case Definition 1.

## **5.10. Medical Resources Use Questionnaire**

See Section 4.11.

### **5.10.1. Analysis Methods**

The PPE set will be used to analyze the medical resource utilization data.

At Day 365 and Day 730 the proportion of participants reporting having used the medical resources by category and subcategory will be summarized per group and per risk level.

The proportion of participants with emerging medical resources utilized, associated with any RT-PCR confirmed RSV ARI or LRTD based on Case Definition 1 across all three RSV seasons, will be summarized per group and per risk level, by MRU category and subcategory. Moreover, for those participants, the number of recorded visits and the length of stay will also be summarized descriptively for the RSV ARI episode.

Finally, the proportion of participants with any RT-PCR confirmed RSV disease with emerging medial resources utilized will be tabulated per group and the corresponding VE (1-relative risk) will be determined as described in Section 5.4.1.2 and graphically depicted with a forest plot, for the second and third RSV season and across season two and three and all three RSV seasons. In case a participant experience two or more RSV ARIs during the three RSV seasons, the same rule will apply similar to a participant experiencing two or more ARIs during the same season (see Section 4.5.1.1).

